#### 10.3 Criteria for Causality Assessment

The causal relationship with the protocol treatment (allogeneic iPS cell-derived corneal epithelial cell sheet transplantation) will be assessed according to the following criteria.

Causal relationship	Criteria for causality assessment			
Not related	There is sufficient information to show that the event is unrelated to the protocol treatment, or the event can be sufficiently explained by the patient's known clinical history.			
Cannot be denied	The event is undeniably correlated with the protocol treatment and cannot be explained by other factors such as the primary disease or a comorbidity, concomitant drug, or concomitant therapy.			
Related	The event is correlated with the protocol treatment, and cannot be explained by other factors such as the primary disease or a comorbidity, concomitant drug, or concomitant therapy. When the protocol treatment is discontinued, the clinical course (e.g., reduced severity or disappearance of the event) indicates that the event was caused by the protocol treatment.			

When the causal relationship with the protocol treatment (allogeneic iPS cell-derived corneal epithelial cell sheet transplantation) is determined to be "related" or "cannot be denied," the cause will be determined as follows.

- 1) Caused by transplantation surgery/procedures
- 2) Caused by the transplanted specific processed cell product (i.e., iCEPS)
- 3) Caused by general anesthesia
- 4) Other

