#### [Rationale for setting]

- 1) To ensure safety of the patients, because antibacterial drugs, corticosteroids, immunosuppressive agents, and anesthetic drugs are necessary for transplantation of iCEPS.
- 2) To ensure safety of the patients, because the possibility of hypersensitivity or allergic reaction induced by residual antibiotics in iCEPS cannot be completely ruled out
- 3) To ensure safety of the patients, because the possibility of hypersensitivity or allergic reaction induced by residual materials of animal origin in iCEPS cannot be completely ruled out.
- 4) To ensure safety of the patients, because use of immunosuppressive agents may exacerbate infections.
- 5) To ensure safety of the patients. In general, malignant tumors can be considered to have been completely cured when there is no recurrence 5 years after treatment.
- 6) To ensure safety of the patients, because glaucoma may worsen because of increase in intraocular pressure by corticosteroid administered after transplantation of iCEPS.

- 7) Diabetes mellitus may be complicated with corneal epithelium disorder or retinal disorder, which may interfere with proper evaluation of efficacy and safety of the protocol treatment.
- 8) To ensure safety of the patients.
- 9) Repeated participation in clinical studies is ethically not acceptable, and such participation may interfere with proper evaluation of efficacy and safety of the protocol treatment.
- 10) General consideration for a clinical research.

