# 6.2 Administration of Medications After iCEPS Transplantation

- 1) All subjects will receive systemic and local corticosteroids and local antibiotics. The medications, dose, and duration of administration may be modified as appropriate based on the subject's condition.
- 2) An immunosuppressive agent (cyclosporine) will be administered after iCEPS transplantation to the following subjects:
  - (1) iCEPS transplantation cases 1 and 2
  - (2) iCEPS transplantation cases 3 and 4, if uncontrolled rejection occurred in 1 or both of the first 2 cases, in accordance with "9.4 Midterm Evaluation"

In general, cyclosporine should be administered from the day of iCEPS transplantation (after transplantation) until Week 52 after transplantation. Trough levels should be checked, and the dose should be adjusted accordingly.

3) Immunosuppressive agents other than cyclosporine (e.g., mycophenolate mofetil) may generally be used during the perioperative period to treat the primary disease.

Compliance with medication and eye drop use will be confirmed by collecting empty medication sheets and bottles from subjects and interviewing the subjects.

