# 10.7 Expected Adverse Events

# 10.7.1 Adverse events caused by transplantation surgery/procedures

1) Conjunctival hyperemia

Treatment: Topical or systemic anti-inflammatory agents

2) Subjective symptoms (eye pain, foreign body sensation, lacrimation, photophobia, dryness, and discomfort)

Treatment: Eye drops, eye ointment, or oral medication for serious cases

3) Superficial punctate keratopathy

Treatment: Eye drops or eye ointment administered locally for serious cases

4) Corneal epithelial defect

Treatment: Eye drops or eye ointment for serious cases

5) Symblepharon

Treatment: Surgical release of adhesions for serious cases

6) Conjunctivalization

Treatment: Eye drops or eye ointment as needed for serious cases

7) Infectious keratitis

Treatment: Antibiotics, antivirals, or antifungals, and surgical treatment as needed

8) Increased intraocular pressure

Treatment: Local or systemic antiglaucoma agents, and surgical treatment as needed

9) Cataract

Treatment: Surgical treatment for serious cases

10) Corneal keratinization

Treatment: Removal of corneal keratinization for serious cases

11) Endophthalmitis

Treatment: Antibiotics, antivirals, or antifungals, and surgical treatment as needed

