#### 13.2.3 Primary endpoint (safety)

Adverse events for which data were collected will be listed for each subject (event name, onset date, outcome date, duration, outcome, severity, seriousness, causal relationship with the protocol treatment, and rationale for causality determination). The number of subjects who experienced the event and the number of events will also be shown for each adverse event. Duration is defined as "outcome date – onset date + 1 (day)." Serious adverse events will be tabulated in a similar fashion.

Neoplastic lesion status and rejection status at each time point will also be listed, along with details of relevant laboratory results.

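### In 10.3 an adverse event with a second possible cause fits neither positive causality label, so the safety listing can understate possible attribution to iCEPS transplantation

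*Combined protocol and SAP*

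**What the plan says.** Section 10.3 assesses each adverse event against the protocol treatment, which 6.1 defines as iCEPS transplantation. There are three labels.

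- *Not related*: "There is sufficient information to show that the event is unrelated to the protocol treatment", or the known clinical history is a sufficient explanation.
- *Cannot be denied*: reserved for events described as "undeniably correlated with the protocol treatment and cannot be explained by other factors such as the primary disease or a comorbidity, concomitant drug"; therapies given alongside are named too.
- *Related*: correlation with the treatment, the same exclusion of other explanations, and a further condition that begins "When the protocol treatment is discontinued, the clinical course" and asks whether that course points to the treatment.

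Only an event with one of the last two labels is then assigned a source: surgery, the cell product, general anesthesia, or other.

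Safety is the primary endpoint (9.1). Section 13.2.3 lists every event by subject, and the listed fields include "causal relationship with the protocol treatment, and rationale for causality determination".

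**The concern.** A three-step causality scale normally uses its middle step for the uncertain case, where treatment is a possible cause and so is something else. Here the middle step is closed to that case. It even asks for undeniable correlation, where the top step asks only for correlation.

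An assessor who applies the text as written to a mixed-cause event has no positive label to give, and *Not related* is the only other entry on the form. The study is first-in-human, uncontrolled and has four planned subjects. No comparator arm can show whether an event would have happened anyway, so readers depend on the assessor's attribution. What is at stake is the accuracy of the causality field and of the source split that depends on it.

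**Working it through.** The plan gives no figure to reproduce. The check sets the sections side by side and asks which label each kind of event can receive.

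**Coverage of the labels.** Cross two questions: whether iCEPS or its surgery is ruled out, and whether another factor could explain the event. This gives 2 × 2 = 4 situations.

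| iCEPS or surgery ruled out? | Other factor could explain it? | Label open as written | Label open after the fix |
|---|---|---|---|
| Yes | Yes | Not related | Not related |
| Yes | No | Not related | Not related |
| No | No | Cannot be denied, or Related if its further condition is met | Unchanged |
| No | Yes | No positive label | Cannot be denied |

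As written, 1 of 4 situations has treatment still possible but no positive label. After the fix it is 0 of 4. This describes the definitions and says nothing about how often such events occur.

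**An event the protocol itself expects.**

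1. Section 10.7.1, headed "Adverse events caused by transplantation surgery/procedures", lists "Increased intraocular pressure" as item 8. Surgery is therefore a recognised cause.
2. The rationale for exclusion criterion 6 in 3.2.2 says "glaucoma may worsen because of increase in intraocular pressure by corticosteroid". A second cause is therefore recognised too.
3. Section 6.2 states: "All subjects will receive systemic and local corticosteroids and local antibiotics". The second cause is present in everyone.
4. Corticosteroid lies outside the protocol treatment as 6.1 defines it. The list of other factors in 10.3 is open-ended, so corticosteroid counts whether or not it is called a concomitant drug.
5. If the assessor judges that corticosteroid could explain a pressure rise, both positive labels are barred. *Not related* is not properly met either: surgery has not been shown to be uninvolved, and a drug given after transplantation is not plainly clinical history. No label fits.

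**A second route.** Item 2 of 10.7.1 lists six subjective symptoms as surgical, and 2.4 attributes the same six to LSCD. If an assessor judges that LSCD explains such a symptom, both positive labels close and the clinical-history limb of *Not related* opens, even though surgery has not been ruled out.

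**Whether *Related* is a fallback.** It is not. It has the same exclusion and also looks to the course after treatment stops. The transplant is a one-time procedure, and the only reversal mentioned is graft removal, in 10.7.2.

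**Reach in the listing.** The fields in 13.2.3 are event name, onset date, outcome date, duration, outcome, severity, seriousness, causal relationship and rationale. The label is 1 of these 9. The counts of subjects and events are made by event and do not use it.

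**The case against.** The strongest reply is that 10.3 asks whether the event *is* explained by something else, not whether it *might* be. Read beside the *Not related* row, which asks for a sufficient explanation, a rival cause that is only possible would leave the event in *Cannot be denied*. This narrows the gap without closing it. Corticosteroid may account fully for a pressure rise while surgery still cannot be ruled out, and both positive labels are then barred.

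A second reply is that the row looks like a translation slip. The label's name carries the wider meaning, 10.4 and 14.5 use the phrase in that sense, and the revision history records an earlier mistranslation corrected in 9.2. That is plausible, and assessors may have followed the name. But no other section corrects the row, and a slip needs the same repair.

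A third reply is that nothing decisive uses the label, and this stands. The primary endpoint is overall incidence. Rejection and neoplastic status are listed separately at each time point. The midterm rule (9.4) uses rejection findings. Disease reporting (10.1.4, 10.6) rests on suspicion of a causal link. The rationale is also listed, so a reader can reassess individual events. The Safety Monitoring Committee (9.6) may be asked about causality, but only for serious events and at the principal investigator's request, so it mitigates the problem without removing it.

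**Conclusion.** The point holds as a defect in one definition. An event that iCEPS or its surgery may have caused, and that another factor could also explain, has no fitting positive label and may be recorded as *Not related*. The causality field in 13.2.3 can then understate possible attribution, and the source split is not made for that event. The size is 1 of 4 logical situations and 1 of 9 listed fields. Event counts, subject counts and overall incidence do not change. The number of actual events affected cannot be derived from the documents and may be 0.

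Three stronger readings are not supported.

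- A reader might infer that follow-up suffers, because 10.4 gives particular attention to events whose causal link cannot be denied. But 10.4 uses that phrase in its ordinary wider sense, and it tracks all adverse events until recovery or until tracking is no longer clinically needed, whatever the label.
- A reader might count raised intraocular pressure, subjective symptoms and conjunctivalization as 3 of the 11 event types in 10.7.1 that are caught in every subject. That would be a matter of judgement. Conjunctival scar is removed as far as possible at surgery (6.1), so new postoperative symptoms or conjunctivalization are not automatically explained by LSCD. Corticosteroid explains a pressure rise only if the assessor so concludes.
- A reader might infer that harm from cyclosporine or corticosteroid alone is mislabelled. It is not. *Not related* is correct for it, given the definition in 6.1.

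The conclusion assumes that assessors apply the printed criteria and not just the label's name.

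**What to change.** In 10.3, define *Cannot be denied* as: iCEPS transplantation (product or surgery) is a possible cause and cannot be ruled out, even if another factor could also explain the event. Keep the no-other-explanation condition for *Related* only. Re-read any labels already assigned against the recorded rationale, and assign a source where a label becomes positive.

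No new cause category for required medication is needed. The existing fourth source, other, and the rationale field already allow a drug contribution to be recorded.

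The cost is a revision of one table row and a short review of recorded labels in a four-subject study. No visit, sample, subject or analysis is added. The downside is that more events may be labelled as not excluded. The corrected row would also serve the later trials foreseen in 2.4.

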# 10.4 Response and Follow-up Investigation After Occurrence of Adverse Events

The investigator or subinvestigator shall provide appropriate first aid to adverse events occurring in the subject participating in the clinical research, pay attention to ensuring the safety of the subject, and take appropriate measures such as receiving a diagnosis by a specialist doctor as necessary, and endeavor to investigate the cause therein.

In addition, the adverse event name, severity, onset date, outcome, outcome date, severity, causal relationship with the protocol treatment, rationale for causality determination, and, if necessary, details of treatment and progress. If the diagnosis name is identified from the signs or symptoms, give priority to the individual signs and symptoms. If the diagnosis name is not identified from the signs or symptoms, each sign and symptom is filled in as an individual adverse event.

The term of adverse events used by subinvestigators is replaced with standard terms using MedDRA/J for aggregation and analysis. The medical validity of the rereading operation is determined by the investigator acting as the subject's physician.

As much as possible, follow-up investigations will be conducted on adverse events that have occurred, particularly events in which causal relationships with the protocol treatment cannot be denied. Adverse events that develop during the clinical research period are tracked until they are recovered or determined to be clinically unnecessary.

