# 9. Definition of Efficacy and Safety Evaluations and Endpoints

# 9.1 Primary Endpoint

Safety will be evaluated by collecting adverse event data.

Evaluation period: From the day of iCEPS transplantation (during transplantation) to Week 52 after iCEPS transplantation or the date of discontinuation

Recording method: The subinvestigator acting as the subject's physician will record the details of each adverse event in the CRF (see "10.4 Response and Follow-up Investigation After Occurrence of Adverse Events"). The subinvestigator and physician-evaluator will make determinations regarding rejection and uncontrollable rejection.

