#### 10.7.2 Adverse events caused by the specific processed cell product (iCEPS)

- 1) Allergic reaction due to use of materials of animal origin (bovine, porcine, or rodent)
  Treatment: Systemic allergic reactions should be treated by systemic antiallergic agents
  and corticosteroids, and shock should be treated by vasopressors and bronchodilators.
- 2) Infectious disease due to use of materials of human and animal origin (bovine, porcine, or rodent)

Treatment: If infectious keratitis is suspected, identification of the causative microorganism by culture of a scraped sample of the lesion and treatment by means such as topical/systemic antibiotics or graft removal may be necessary.

3) Immunological rejection

Treatment: Immunosuppressive agents and corticosteroids may be required.

- 4) Development of a neoplastic lesion
  - (1) Local (at site of iCEPS transplantation)

Treatment: Although this is considered extremely unlikely, if it does occur, appropriate treatment should be given based on the type of lesion.

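### Section 10.4 ranks signs and symptoms above an identified diagnosis, so one diagnosed event, chiefly an infection, can be split or lose its name in the primary safety counts

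*Combined protocol and SAP*

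**What the plan says.** Section 9.1 sets the only primary endpoint: "Safety will be evaluated by collecting adverse event data".

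Section 10.4 governs how an event is named on the case report form. When a diagnosis can be made: "If the diagnosis name is identified from the signs or symptoms, give priority to the individual signs and symptoms". When it cannot: "If the diagnosis name is not identified from the signs or symptoms, each sign and symptom is filled in as an individual adverse event". The names entered are then coded: "The term of adverse events used by subinvestigators is replaced with standard terms using MedDRA/J for aggregation and analysis".

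Section 13.2.3 builds the primary safety output from those entries. Each event is listed by subject with its dates, severity, seriousness and causality, and "The number of subjects who experienced the event and the number of events will also be shown for each adverse event". The same section adds a second output: "Neoplastic lesion status and rejection status at each time point will also be listed, along with details of relevant laboratory results".

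Two other places treat diagnoses as named entities. Section 9.1 requires an assessment of rejection: "The subinvestigator and physician-evaluator will make determinations regarding rejection and uncontrollable rejection". Section 10.7 lists expected adverse events, among them infectious keratitis and endophthalmitis (10.7.1) and "Immunological rejection" (10.7.2).

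**The concern.** A rule that separates diagnosed from undiagnosed cases should treat them differently. This one does not: whether or not the clinician reaches a diagnosis, the signs are what is recorded.

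The recorded unit fixes every row of the per-event table, so the rule can do three things to the primary endpoint:

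- It can turn one clinical episode into several events.
- It can leave the diagnosis term with no subjects, although section 10.7 names that diagnosis as an adverse event.
- It can blur attribution. Corneal epithelial defect is an expected event of the surgery in section 10.7.1 and is also one of the rejection findings in section 9.4, whereas rejection is an expected event of the cell product in section 10.7.2. Under section 10.3 the cause is assigned event by event, so a sign entered alone may be credited to the procedure. Nothing forces that result, but in a first-in-human product study the distinction matters.

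**Working it through.** The plan gives no figure to reproduce. Section 13.3 rules out tests and estimation. The check is a comparison of sections and a short count.

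**Step 1: the two branches of section 10.4.** Diagnosis identified: signs and symptoms have priority. Diagnosis not identified: each sign and symptom is its own event. The condition has no effect on what is recorded.

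**Step 2: the path to the primary table.** Recorded term (10.4), then MedDRA/J term (10.4), then subjects and events per term (13.2.3). No step regroups signs under a diagnosis.

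**Step 3: count for one rejection episode.** Inputs:

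- Subjects: N = 4 (section 7).
- Findings used to judge rejection: three, namely stromal edema, ciliary injection and epithelial defect (section 9.4).
- Assumption: one episode in one subject, with k of the three findings present, k = 1 to 3. Section 9.4 calls for an overall judgement and sets no minimum.
- Assumption: the signs are entered in place of the diagnosis.

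| Quantity | Section 10.4 as written | Diagnosis recorded first |
|---|---|---|
| Events entered | k = 1, 2 or 3 | 1 |
| Surplus events | k − 1 = 0, 1 or 2 | 0 |
| Subjects under rejection, per-event table | 0/4 | 1/4 = 25% |
| Subjects under rejection, separate status listing | 1/4 | 1/4 |

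At k = 1 the event count is right but the name is lost. At k = 3 the count is three times too high. In every case the per-event table and the status listing disagree, 0/4 against 1/4, and no section says how to reconcile them.

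**Step 4: the same count for an infection.** The documents do not list the signs that make up keratitis or endophthalmitis, so the number of entries cannot be given. With s signs there would be s entries instead of 1, and again 0/4 instead of 1/4 subjects under the diagnosis.

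**Step 5: which diagnoses have a second named output.** Rejection and neoplastic lesions do, in section 13.2.3. Infectious keratitis and endophthalmitis do not. Many other items in section 10.7.1, such as conjunctival hyperemia, superficial punctate keratopathy and raised intraocular pressure, are themselves signs or single findings, and the rule leaves them unchanged.

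**The case against.** The other side has good arguments.

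**A slip, not a method.** The first sentence makes sense only if the diagnosis was meant to come first. The same paragraph contains an incomplete sentence that lists severity twice, and the revision history records that version 1.3 corrected a mistranslation in section 9.2. Inversion is plausible. The documents cannot settle it, and the text in force is still the text that staff would follow.

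**Priority is not prohibition.** The wording does not forbid entering the diagnosis as well. That stands, and it makes the 0/4 figure conditional. If both were entered, however, the episode would be counted under its diagnosis and its signs together.

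**No planned decision uses the count.** There are four subjects with line listings, so signs sharing a date would be visible. The regimen for cases 3 and 4 rests on the rejection determination in section 9.4, and stopping under section 11.1 rests on judgement or on authorities. This limits the harm, but the per-event counts are still a stated output of the sole primary endpoint.

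**Infections have another route.** An infection suspected to come from the product also triggers a report under section 10.6. That report is not part of the primary analysis.

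Three stronger readings are tempting and are not supported:

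- A reader might infer that rejection never appears by name in the primary analysis. It does: section 13.2.3 lists its status at each time point and section 9.1 requires two assessors to determine it.
- A reader might take the threefold count as the expected result. It is the maximum.
- A reader might conclude that events in this trial were in fact split. The supplement's adverse event tables (S8 and S9) and the separate case report form guidance named in section 12.1 are not in the text available, so actual recording cannot be checked.

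**Conclusion.** The point holds as a defect in an operative recording rule. Section 10.4 leads to sign-level recording in both branches and conflicts with section 10.7, which names diagnoses as adverse events.

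Its size is modest. For one rejection episode in one of four subjects, the effect is 1 to 3 entries instead of 1, and 0/4 instead of 1/4 subjects under the diagnosis term in the per-event table. That rests on the rule being followed literally, with signs replacing the diagnosis. The separate listing keeps rejection and neoplastic lesions visible, so for rejection the problem is a possible disagreement between two primary outputs. The real loss falls on infections such as keratitis and endophthalmitis, which no other planned output of the primary endpoint restores by name. Section 12.4 also allows adverse event details entered directly on the case report form to serve as source, so a diagnosis left off the form may have no other record.

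**What to change.** - **Section 10.4 and the case report form guidance:** when a diagnosis is identified, it is the recorded adverse event term, with its signs and symptoms attached to it. Signs and symptoms are separate events only when no diagnosis is made.
- **Section 13.2.3:** add one sentence saying that the rejection and neoplastic lesion listing is reconciled with the adverse event table.
- **Data:** before data lock, check the four subjects' entries and re-code only where one diagnosed episode was split. Take the handling to the Clinical Case Conference in section 13.4, and revise the protocol and explain the change in the clinical study report as section 13.5 requires. If the data are already locked, make the check a documented correction in that report.

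The cost is one reworded rule, one added sentence and a review of four subjects' forms. No new data are needed.
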